1.2 Prostacyclin and pulmonary hypertension

Prostacyclin (Prostaglandin I₂ / PGI₂), a metabolite of arachidonic acid, is formed via the cyclooxygenase pathway. Endothelial cells are the main source of PGI₂ and its action is directed to both the local vascular wall and to blood cells, particularly those that adhere to the endothelium. It is a potent endogenous vasodilator, inhibitor of platelet aggregation and smooth muscle cell proliferation through its activity at the prostacyclin (IP) receptor [O'Grady 1980].

The IP receptor is a G protein-coupled receptor (GPCR) that activates adenylate cyclase, leading to increased cyclic adenosine monophosphate (cAMP) levels in the target cells. cAMP has been widely implicated in the control of pulmonary vascular tone and inhibition of mitogenic pathways in vascular smooth muscle cells.

Patients with PAH have been shown to have a deficiency of PGI₂ [Christman 1998] and of PGI₂ synthase [Tuder 1999] causing an imbalance in PGI₂ and thromboxane A₂ (TXA₂), its physiological antagonist. These findings led to the rationale that targeting the PGI₂ pathway with IP receptor agonists could be beneficial.

The first, epoprostenol, the chemical analog of PGI₂, was approved in 1996 for NYHA/WHO functional class III-IV IPAH and PAH associated with scleroderma, and was shown to improve exercise tolerance and survival in patients with IPAH [Barst 1996]. Since continuous intravenous epoprostenol became available, the prognosis for patients suffering from PAH has significantly improved. However, due to its short half-life and chemical instability, long-term epoprostenol therapy requires a permanently implanted central venous catheter and a portable infusion pump, exposing patients to a series of complications including catheter-related embolism or thrombosis, infection, and delivery system malfunctions resulting in poorly tolerated overdosing or underdosing.

The complexity of epoprostenol therapy has led to attempts to develop other prostanoids with simpler modes of delivery. Treprostinil, a stable PGI₂ analog with a half-life of 3 h, has been developed for intravenous, subcutaneous delivery, and inhalation. It has beneficial effects on exercise and hemodynamics, which depend on the dose achieved. This, in turn, is determined by the patient's ability to tolerate the drug's side effects. Iloprost, another PGI₂ analog, has been approved for intravenous delivery and inhalation. Inhaled iloprost shows some selectivity of the hemodynamic effects to the lung vasculature, thus reducing systemic side effects, but has to be inhaled between 6 to 9 times per day, which may limit compliance.

The inconveniences of the administration routes of the above-mentioned drugs, such as injection site pain and reaction (redness and swelling) for subcutaneous administrations, or line infections, sepsis, hematoma, and local pain for intravenous infusions, are another factor influencing the patient's benefit from these treatments.

1.3 Selexipag – a non-prostanoid IP receptor agonist

Selexipag is an orally available drug that is readily hydrolyzed to the active metabolite ACT-333679. Both selexipag and ACT-333679 are potent and selective agonists at the human IP receptor.

ACT-333679 has a 13-fold higher affinity for the human IP receptor [Selexipag IB] and is 15-fold more potent than selexipag in activating the human IP receptor. *In vitro* studies showed that ACT-333679 has at least 130-fold lower affinity for other human prostanoid receptors such as the prostaglandin E₁₋₄, D₂, and F₂ receptors, as well as the TXA₂.

Selexipag has been selected for further clinical development based on its pharmacokinetic (PK) profile observed in Phase 1 studies and the results from the Phase 2 study [Section 1.3.2].

1.3.1 Preclinical information

In vivo pharmacology studies demonstrated that orally administered selexipag significantly reduced right ventricular systolic pressure (RVSP) and right ventricular hypertrophy (RVH) in a rat model of PAH. Selexipag also ameliorated the impaired relaxant response of the pulmonary artery from these animals.

Furthermore, selexipag significantly increased survival of rats with monocrotaline-induced PAH [Kuwano 2008].

In normotensive rats prolonged administration of selexipag did not attenuate the acute increase in femoral skin blood flow induced by the compound, suggesting lack of desensitization of the IP receptor [Kuwano 2007].

1.3.2 Clinical information

1.3.2.1 Phase 1 studies in healthy subjects

During the Phase 1 program selexipag was well tolerated after single and multiple daily oral doses of up to and including 1600 µg b.i.d. No serious adverse events (SAEs) were reported in any of the Phase 1 studies and the majority of the adverse events (AEs) were of mild intensity. The most frequently reported AEs were headache, myalgia, jaw pain, dizziness, nausea, vomiting, arthralgia, diarrhea, and abdominal pain. No clear dose relationship could be established for the above-mentioned AEs.

Multiple doses of selexipag up to 1600 µg b.i.d. (study AC-065-101), starting with 400 µg b.i.d. and up-titrated in increments of 200 µg every 3rd day, were well tolerated. Most AEs were mild or moderate in intensity. The incidence of AEs was similar for all treatment groups, which suggests improved tolerability after repeated dosing. Tolerability decreased at a dose of 1800 µg selexipag b.i.d. and led to an increase in moderate AEs (headache, myalgia, and nausea) that required concomitant medication. The maximum dose tested in Japanese subjects was 600 µg b.i.d. There were no consistent differences in the number and type of AEs with increasing dose of selexipag.

Treatment with selexipag up-titrated in increments of 200 µg to 1800 µg (the highest dose tested in Caucasian subjects) or 600 µg (the highest dose tested in Japanese subjects) (study AC-065-101 and NS304/P1/01), were not associated with clinically relevant changes in systolic and diastolic blood pressures, heart rate, electrocardiogram (ECG) intervals and morphology, vital signs and laboratory tests. In addition, in the AC-065-101 study, no changes were observed in thyroid markers, orthostatic hypotension, platelet aggregation test, bone formation, bone resorption markers, and coagulation markers.

Plasma concentration-time profiles and PK parameters of selexipag and ACT-333679 were comparable across the studies performed in healthy subjects. The plasma concentration-time profiles of selexipag revealed that, in general, maximum plasma concentrations were achieved in about 1–2 h after single-dose and multiple-dose administration. Thereafter, plasma concentrations of selexipag decreased quickly. The plasma concentration-time profiles of ACT-333679 showed that, in general, maximum plasma concentrations were achieved in about 3–4 h after single- and multiple-dose administration. Thereafter, plasma concentrations of ACT-333679 compared to selexipag decreased more slowly. In the study AC-065-101 the exposure (area under the concentration-time curve [AUC]) to ACT-333679 is approximately four times higher than to selexipag.

Following multiple oral administrations of selexipag, the apparent elimination half-lives of selexipag and its active metabolite ACT-333679 were between 0.9 and 1.9 hours and

between 7.9–14.5 h, respectively, which supports twice daily oral administration. The PK of selexipag, after both single- and multiple-dose administration, were approximately dose-proportional over the tested dose range, i.e., up to a single dose of 800 µg and multiple doses of 1800 µg b.i.d. of selexipag. After multiple-dose administration, steady-state conditions of selexipag and ACT-333679 were reached on Day 3. No relevant accumulation in plasma either of selexipag or ACT-333679 occurred after multiple-dose administrations.

Results from study QGUY/2006/NS304/-01 indicate that food intake delayed the exposure to ACT-333679, as the median t_{max} increased from 2.5 hours during fasting to 4 hours in fed state, and decreased the exposure to ACT-333679 by 27%.

More subjects reported AEs in the fasted period than in the fed period. These results may indicate better tolerability of selexipag when administered with food.

Selexipag did not influence the PK or pharmacodynamics (PD) of warfarin. Similarly, co-administration of warfarin with selexipag did not have an impact on the exposure to selexipag or its active metabolite ACT-333679.

The metabolism and excretion of selexipag were studied following a single dose administration of radioactively labeled ACT-293987A (400 µg) (study 186933). 105% of the radioactivity was excreted primarily via feces (93%) and urine (12%). Excretion was complete after 5 days indicating no relevant retention of drug-related material in man.

When comparing the PK of selexipag and ACT-333679 from study QGUY/2006/NS30/-01, which mainly included Caucasian subjects, to those of study NS304/P1/01, which included only Japanese subjects, the concentrations of both selexipag and ACT-333679 were higher in Japanese subjects. The difference in the PK was mainly due to the difference in body weight. When corrected for body weight a small residual difference was observed, however this difference was within one standard deviation of the mean and not consistent between the different dose levels. The clinical relevance of this observation is currently unknown.

In study AC-065-102, investigating the photosensitizing potential of selexipag, doses of 800 and 1200 µg selexipag did not show any difference in the phototoxic index compared to placebo and the mild photosensitizing agent ciprofloxacin. The study did not indicate that selexipag has clinically relevant photosensitizing potential in humans.

Results of study AC-065-113 (Part I) showed that in the presence of multiple-dose gemfibrozil (600 mg b.i.d.), a strong CYP2C8 inhibitor, a 2-fold increase in selexipag exposure and 11-fold increase in ACT-333679 exposure was observed.

Results of study AC-065-113 (Part II) showed that concomitant administration of selexipag and multiple-dose rifampicin (600 mg once daily; a moderate inducer of CYP2C8) led to no relevant change in exposure to selexipag in terms of AUC, while exposure to the active metabolite in terms of AUC decreased by half.

Results of study AC-065-117 showed that concomitant administration of selexipag (200 µg b.i.d.) with clopidogrel (300 mg as a loading dose or maintenance doses of 75 mg once daily), a moderate inhibitor of CYP2C8, had no relevant effect on the exposure to selexipag but increased the exposure to the active metabolite by approximately 2.2-fold and 2.7-fold following loading dose and maintenance dose, respectively.

The effects of strong inhibitors of UGT1A3 and UGT2B7 on the exposure to selexipag or its active metabolite have not been studied. Concomitant administration may result in a significant increase in exposure to selexipag or its active metabolite.

Results of the completed Phase 1 studies are described in the current version of the Investigator's Brochure [[Selexipag IB](#)].

1.3.2.2 Phase 2 studies in patients with pulmonary arterial hypertension

A Phase 2a proof-of-concept study in PAH (NS-304/-02) was completed in July 2009. Study NS-304/-02 was conducted in seven European centers and enrolled 43 patients with PAH, who were randomized in a 3:1 ratio to selexipag (n = 33) or placebo (n = 10). All enrolled patients received double-blind study treatment, which was prematurely discontinued in three patients (two on selexipag and one on placebo). Median exposure to study treatment was 146 days in the placebo group and 149 days in the selexipag group. For most patients, PAH was idiopathic (70% and 73% of patients in the placebo and selexipag groups, respectively). At baseline, all patients were receiving either an ERA (bosentan, 70% and 61% of patients in the placebo and the selexipag group, respectively, or sitaxentan in four patients in the selexipag group only) or a PDE-5 inhibitor (sildenafil 60% and 64% of patients in the placebo and the selexipag group, respectively). Three patients in the placebo group (30%) and 12 patients in the selexipag (36%) were receiving both an ERA and a PDE-5 inhibitor.

After 17 weeks of treatment, mean PVR was decreased from baseline in the selexipag group ($-168 \pm 45 \text{ dyn}\cdot\text{sec}/\text{cm}^5$) and increased in the placebo group ($137 \pm 35 \text{ dyn}\cdot\text{sec}/\text{cm}^5$). Values at Week 17 expressed as a percent of baseline values showed a significant 30.3% reduction in PVR with selexipag compared with placebo ($P = 0.0045$, Wilcoxon rank sum test). Similar improvements in PVR were observed in the all randomized analysis set.

After 17 weeks of treatment, the mean 6-minute walk distance (6MWD) increased from baseline in the selexipag group ($+24.7 \pm 12.9$ meters) and was unchanged in the placebo group ($+0.4 \pm 8.9$ meters), which resulted in a mean treatment effect of 24.2 ± 23.7 meters ($P = 0.2218$, Wilcoxon rank sum test). Three subjects showed aggravation of PAH during the double-blind study, two patients in the placebo group (20%) and one (3.3%) patient in the selexipag group. All three patients were in NYHA/WHO functional class III at baseline. A statistically significant increase of Cardiac Index was observed in the selexipag group when compared to a decrease in the placebo group, which resulted in a mean treatment effect: 0.48 ± 0.17 L/min/m², (\pm standard error) ($P = 0.0137$, Wilcoxon rank sum test). A statistically significant decrease of systolic vascular resistance (SVR) was observed in the selexipag group when compared to an increase in the placebo group, which resulted in a mean treatment effect: -407.8 ± 164.2 dyn·sec/cm⁵, (\pm standard error) ($P = 0.0071$, Wilcoxon rank sum test).

Ten (100%) patients in the placebo group reported a total of 39 treatment emergent-adverse events, whilst 31 (93.9%) patients in the selexipag group reported a total of 182 adverse events (AE). The most frequently reported AE in the active group was headache, reported in 22 (66.7%) patients in the selexipag compared to two (20%) patients in the placebo group. In the selexipag group, pain in jaw, pain in extremity, nausea, diarrhea, flushing, dizziness, cough and myalgia were reported in 12 patients (36.4%), 10 patients (30.3%), nine patients (27.3%), six patients (18.2%), six patients (18.2%), five patients (15.2%), four patients (12.1%) and four patients (12.1%), respectively. Most AEs in both treatment groups were of mild or moderate intensity, but a severe event was experienced by a larger proportion of patients on placebo (40%) than in the selexipag group (18.2%). Seven SAEs were reported in four patients (40%) in the placebo group. Fourteen SAEs were reported in six patients (18.2%) in the selexipag group. There were no changes from baseline to the end of treatment in either systolic or diastolic blood pressure, or in pulse rate in the placebo group and in the selexipag group. The analysis of marked laboratory abnormalities (MLA) in the selexipag compared to the placebo group did not reveal any relevant increase of the incidence of MLA after selexipag treatment. No clinically relevant ECG changes were observed in either treatment group.

Results of completed studies are described in the current version of the IB [[Selexipag IB](#)].

1.4 Study rationale

1.4.1 Medical and regulatory background

Selexipag is a new, selective, orally active non-prostanoid IP receptor agonist selected for clinical development in PAH.

Prostacyclin (epoprostenol) and analogs like treprostinil (intravenous, subcutaneous, and inhaled) and iloprost (inhaled) have been approved for the treatment of PAH. However, the administration routes are not always convenient. For subcutaneous administrations, injection site pain and reaction (redness and swelling) occur in the majority of patients. For intravenous infusions, line infections, sepsis, hematoma, and local pain are most common. Inhaled iloprost has to be given between 6 to 9 times per day, which may limit compliance. An orally available medicinal product, such as selexipag, which, by targeting the prostacyclin pathway could affect the progressive course of PAH, would represent an important advancement in the clinical management of PAH patients, and provide a significant contribution in the treatment options for these patients.

To date, several medicinal products have been approved for the treatment of pulmonary hypertension (PH), specifically PAH. The majority of controlled trials performed in PAH have been relatively short-term studies in selected populations.

The main objective of the AC-065A303/GRIPHON OL study will be to assess the long-term safety and tolerability of selexipag in patients with PAH.

1.4.2 Patient population

The patient population will consist of:

- Patients who have completed the double-blind study AC-065A302/GRIPHON as scheduled per protocol (i.e., treated until unblinding of the study).
- Patients experiencing a morbidity event (confirmed by the Critical Event Committee [CEC]) during the study AC-065A302/GRIPHON.
- Patients who have experienced a worsening of PAH during the Treatment Extension period of AC-065A302/GRIPHON and for whom a written approval to enter this study has been obtained from the sponsor.

1.4.3 Study design

The study is designed as an open-label, non-comparative, multicenter study following the AC-065A302/GRIPHON study to assess long-term safety and tolerability of selexipag in patients with PAH.

1.4.4 Comparative drug(s) and/or placebo

Not applicable

1.4.5 Dose selection

Up-titration to the individual patient's highest tolerated dose appears to be the most adequate treatment regimen for IP receptor agonists, including epoprostenol (i.v.), treprostinil (i.v., s.c. and inhaled) and iloprost (inhaled). Starting with high doses of these compounds is associated with poor tolerability due to typical prostanoid-associated

pharmacological effects such as headache, myalgia, flushing, nausea, and vomiting. Clinical experience with IP receptor agonists has shown that it is important to start at lower doses and up-titrate in order to improve tolerability.

This approach is used in the AC-065A302/GRIPHON study and will be kept in the open-label study.

During AC-065A303/GRIPHON OL, the selexipag starting dose will depend on the dose of selexipag received during AC-065A302/GRIPHON as well as at which time point of AC-065A302/GRIPHON patients are enrolled in AC-065A303/GRIPHON OL:

- Patients who enter AC-065A303/GRIPHON OL following a morbidity event during AC-065A302/GRIPHON (confirmed by the CEC) and patients experiencing a worsening of PAH during the Treatment Extension period of AC-065A302/GRIPHON for whom a written approval to roll over into this study has been obtained from the sponsor will be transferred without knowledge of their previous study treatment allocation (selexipag or placebo) to preserve the integrity of the double-blind study. Therefore all these patients will enter the titration period, i.e. start treatment with selexipag at the lowest dose (200 µg b.i.d.) and will be up-titrated until their individual highest tolerated dose is reached. During the maintenance period they will receive selexipag at their individual highest tolerated dose.
- Patients who enter AC-065A303/GRIPHON OL after AC-065A302/GRIPHON Study Closure and completion of the Treatment Extension period will enter the study with knowledge of their previous study treatment allocation (selexipag or placebo) following unblinding of AC-065A302/GRIPHON:
 - Patients who were receiving selexipag will remain on the same dose they were receiving at the end of the AC-065A302/GRIPHON Treatment Extension period. If the treatment with selexipag was interrupted for 3 days or more between the last intake in study AC-065A302/GRIPHON and the initiation of selexipag in AC-065A303/GRIPHON OL, the patient will have to enter the titration period (i.e. start treatment with selexipag at the lowest dose 200 µg b.i.d.);
 - Patients who were receiving placebo will enter the titration period and start selexipag at the lowest dose (200 µg b.i.d.), and will be up-titrated until their individual highest tolerated dose is reached. They will receive selexipag at their individual highest tolerated dose during the maintenance period.

The dose of patients who did not reach the maximum of 1600 µg b.i.d. can be up-titrated based on the investigators' medical judgment, only after a site visit (scheduled or unscheduled) and in increments of 200 µg b.i.d. each time. The dose can be reduced at any time if the investigator identifies a tolerability concern for a patient.

The dose of the study drug must be up-titrated again in any case if the patients' treatment is interrupted 3 days or more between the last visit in study AC-065A302/GRIPHON and the start of study AC-065A303/GRIPHON OL, or within study AC-065A303/GRIPHON OL [Section 3.4.1].

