3.2.4 Concomitant medications

3.2.4.1 Allowed concomitant medications

PAH-specific therapies including ERAs, PDE-5 inhibitors, and/or riociguat.

Concomitant use of inhaled, i.v., and s.c. prostacyclin and prostacyclin analogs (e.g., epoprostenol, treprostinil, iloprost) is permitted, as deemed medically indicated by the

³ A woman is considered to have childbearing potential unless she meets at least one of the following criteria:

- previous bilateral salpingo-oophorectomy or hysterectomy
- premature ovarian failure confirmed by a specialist gynecologist
- pre-pubescence, XY genotype, Turner syndrome, uterine agenesis
- age > 50 years with amenorrhea for at least 24 consecutive months prior to screening

⁴ Single administration of i.v./inhaled prostacyclin or analogs used for acute vasodilator testing during a RHC procedure is allowed.

investigator, to stabilize a patient with worsening of PAH or to switch a patient to i.v. or s.c. treatment.

If a patient is scheduled for an intervention that may temporarily prevent him/her from taking oral medications, it is allowed to interrupt selexipag treatment and temporarily switch to another IP receptor agonist medication with a more convenient route of administration with regard to the patient's medical condition. The patient will be allowed to restart selexipag once he/she can take oral medications again. When re-starting selexipag, it is recommended to begin with the lowest dose (i.e., 1 tablet/200µg b.i.d.) and to progressively increase the selexipag dose to reach the maximum dose that was previously tolerated by the patient. The decrease of the other IP receptor agonist dose will be done in parallel with the increase of selexipag dose based on patient's individual tolerability. If the patient experiences pharmacological side effects that cannot be tolerated while he/she is concomitantly taking selexipag and the other IP receptor agonist medication, a dose reduction or stop of this other IP receptor agonist will be considered before considering a dose reduction or a stop of selexipag.

Single administration of i.v./inhaled prostacyclin or analogs used for acute vasodilator testing during a right heart catheterization (RHC) procedure is allowed.

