3.3.2 Study drug up-titration

The study drug must be up-titrated to each individual patient's highest tolerated dose in the range of 200 µg to 1600 µg b.i.d.

Patients whose dose needs to be up-titrated will start with one tablet of selexipag (200 µg) b.i.d. from Day 1. If this dose is well tolerated, the dose will be up-titrated by the investigator in 200 µg increments at weekly intervals during scheduled telephone calls or visits until reaching the patient's highest tolerated dose.

The decision to stop further up-titration of the dose will be based on the investigators' medical judgment, based on the occurrence and severity of typical pharmacological effects of IP receptor agonists, such as headache, jaw pain, myalgia, flushing and nausea, which cannot be tolerated by the patient. The dose will then be reduced by 200 µg b.i.d, if needed.

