3.4 Study drug discontinuation and study withdrawal

3.4.1 Study drug interruption or permanent discontinuation

The investigator must interrupt or permanently discontinue the study drug if continued administration is believed to be contrary to the best interest of the patient.

In case liver impairment is suspected, a clinical assessment of severity (e.g., Child-Pugh score) should be performed. If the investigator becomes aware that a patient has developed moderate hepatic impairment (e.g., Child-Pugh B) at any time during the AC-065A302/GRIPHON or the AC-065A303/GRIPHON OL study, then it is the responsibility of the investigator to evaluate the benefit-risk of keeping the patient on study drug. In case a patient has developed severe hepatic impairment (e.g., Child-Pugh C), the study drug must be discontinued. Assessment of Child-Pugh score is not a mandatory study assessment.

Should signs of pulmonary edema occur, the possibility of associated pulmonary veno-occlusive disease should be considered. If confirmed, selexipag must be discontinued.

The interruption or permanent discontinuation of study drug might be triggered by an AE, a diagnostic or therapeutic procedure, an abnormal assessment (e.g., ECG or laboratory abnormalities), or for administrative reasons, in particular withdrawal of the patient's consent. The reason for study drug interruption or permanent discontinuation must be documented in the CRF.

Any study drug interruption of 3 days or more will require new up-titration. Patients will start again with 1 tablet of selexipag (200 µg) b.i.d. If this dose is well tolerated, the dose will be up-titrated by the investigator in 200 µg increments up to the patient's highest tolerated dose before study drug interruption. For each patient, the up-titration frequency will be up to the medical judgment of the investigator and based on his/her clinical evaluation of the patient's tolerability to study drug prior to its interruption.

Interruptions of 1 day and more must be recorded on the study drug log in the CRF.

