5.5.1.1. Definition of IMTD

The IMTD (mcg b.i.d.) is defined by the following rules regardless of length of the titration period:

- Participants who entered the study defined maintenance period (=who completed the study titration period, Section 6.10):
 - IMTD is defined as the last b.i.d. dose at the end of titration period
- Participants who did not enter the study defined maintenance period (=who withdrew from the study during the study titration period, Section 6.10):
 - IMTD is defined as the highest b.i.d. dose without dose reduction afterward.
 - If no up-titration attempted, IMTD is defined as zero.

The IMTD (mcg b.i.d.) categories are defined for both STS (A302+A303) and OLS as

- 0
- 200-400
- 600-1000
- 1200-1600

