6.10. Appendix 10 Titration and maintenance periods

In the A302 CSR SAP, titration and maintenance periods are defined as follows:

- The study intervention Titration Period starts at date of first intake of study intervention and ends at Day 86 (or earlier, if selexipag is discontinued before). Study Day 86 has been chosen according to the study protocol-specified maximum duration of the Titration Period including a 3 days tolerance.
- The study intervention Maintenance Period starts at Day 87 and ends at the date of last intake of study intervention.

Note: The definition of titration/maintenance period in the A303 protocol is not clear, in fact in Section 3.10.2.10 it seems that Week 16 is included in the titration period. For OLS and STS (A302+A303), titration period should be considered to end at Week 12 as defined in the summary of clinical safety (SCS) of the first NDA/MAA submission in 2014. In the A302 protocol, the first dose was to be given in the afternoon at study day 1 with an exposure duration of 0.5 day. Thus, the duration of titration period, for participants who did not prematurely stop the study intervention during the titration period, was considered as 86.5 days in the SCS for the first NDA/MAA. However, for the onset of adverse events only the date (without time) was collected. In addition, data of study drug log in CRF cannot distinguish whether a patient received afternoon dose only or both morning and afternoon doses. Therefore, the SCS for the sNDA/MAA submission in 2020, RMPs and newly completed selexipag studies were summarized without using such half-day convention and the titration period ended at day 86.

Participants who entered A303 might have experienced a titration period in A302 and another titration period in A303. For STS (A302+A303), only the first titration period with Selexipag is taken, i.e., for participants who received Selexipag already in A302, the titration period in A302 is taken; for participants who received Selexipag only in A303, the titration period in A303 is taken.

For OLS, for participants who received Selexipag in A302 and A303, the titration period in A303 is taken; for participants who received Selexipag only in A303, the titration period in A303 is taken. In case a participant received Selexipag in A302 and A303 but without titration in A303, the entire A303 period is considered as maintenance, hence no titration period in OLS.

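### When re-titration after an interruption of 3 days or more is unfinished on Day 86, the SAP records a passing dose step as the individual maximum tolerated dose

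*Protocol*

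**What the plan says.** **Protocol.** Section 1.4.5 states: "The dose of the study drug must be up-titrated again in any case" where treatment is interrupted for 3 days or more, whether between the two studies or within the open-label study. Section 3.4.1 repeats this: "Any study drug interruption of 3 days or more will require new up-titration". It then gives the restart: "Patients will start again with 1 tablet of selexipag (200 µg) b.i.d". The stated target is the highest dose the patient tolerated before the interruption. The pace is not fixed: "the up-titration frequency will be up to the medical judgment of the investigator". First titration, by contrast, proceeds "in 200 µg increments at weekly intervals during scheduled telephone calls or visits" (3.3.2).

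Section 3.2.4.1 covers a restart after a temporary switch to another IP receptor agonist. Its wording is softer: "it is recommended to begin with the lowest dose".

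**SAP.** Section 6.10 says that the titration period "starts at date of first intake of study intervention and ends at Day 86 (or earlier, if selexipag is discontinued before" that day. Under 5.5.1.1, for anyone who entered maintenance, "IMTD is defined as the last b.i.d. dose at the end of titration period". That section applies its rules whatever the length of titration. Its other branch, which looks for the highest dose not followed by a reduction, is only for participants who left during titration. Section 6.10 deals with a second titration across the two studies, but not with one inside the first 86 days.

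**The concern.** The protocol treats the dose before the gap as the tolerated dose and re-titration as the way back to it. The SAP reads one dose on a fixed calendar day. If the participant is still climbing on that day, the value read is a scheduled step and not a limit of tolerance. If the participant is off drug on that day, the SAP does not say which dose counts.

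The interruption need not reflect intolerance. Protocol 3.4.1 also names diagnostic or therapeutic procedures and administrative reasons.

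IMTD is the only dose summary in SAP 5.5.1, and it stratifies treatment duration. A participant filed too low takes all later exposure, possibly years of it, into the wrong dose category.

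**Working it through.** **Inputs**
- Dosing scheme: start at 200 µg b.i.d., +200 µg b.i.d. weekly, maximum 1600 µg b.i.d. (Protocol 3.3.2, 3.3.3).
- Restart at 200 µg b.i.d. after 3 or more days off (Protocol 3.4.1).
- End of titration: Day 86 (SAP 6.10).
- IMTD categories: 0, 200-400, 600-1000, 1200-1600 µg b.i.d. (SAP 5.5.1.1).
- Assumption: re-titration steps every s = 7 days, as in first titration. s = 3 and s = 1 show the range, because the protocol leaves the speed open.

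**Step 1: the protocol's own figure.** The dose 200 × (k + 1) starts on Day 1 + 7k. For k = 1, 2, 3 this gives Days 8, 15 and 22, as in Protocol 3.3.3. For k = 7 it gives 1600 µg on Day 50, which is Week 7, also as tabulated.

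**Step 2: dose on Day 86 after a restart on Day R.**

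Dose = min(prior dose, 200 × (1 + floor((86 − R) / s)))

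With s = 7 and prior dose 1600:
- R = 37: floor(49/7) = 7, so 1600. Complete.
- R = 38: floor(48/7) = 6, so 1400. Incomplete.
- R = 51: floor(35/7) = 5, so 1200. Category kept.
- R = 52: floor(34/7) = 4, so 1000. Category lost.
- R = 73: floor(13/7) = 1, so 400. Category 200-400.

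**Step 3: last restart day that still regains the prior dose by Day 86.**

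| Prior dose (µg b.i.d.) | s = 7 | s = 3 | s = 1 |
|---|---|---|---|
| 600 | 72 | 80 | 84 |
| 800 | 65 | 77 | 83 |
| 1000 | 58 | 74 | 82 |
| 1200 | 51 | 71 | 81 |
| 1600 | 37 | 65 | 79 |

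The 1200-1600 category is lost from restart Day 52 (s = 7), 72 (s = 3) or 82 (s = 1). The 600-1000 category is lost from Day 73, 81 or 85.

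**Step 4: what can happen on the protocol schedule.** Weekly re-titration to 1600 takes 7 × 7 = 49 days. From Day 50, when 1600 is first reached, only 86 − 50 = 36 days remain, so it cannot finish. For someone on the weekly scheme who is off drug for exactly 3 days and then steps weekly, the Day 86 dose is below the pre-interruption dose only if the last dose before the gap was on Day 43 or later. On Day 43 the prior dose is 1400, restart is Day 47, and floor(39/7) = 5 gives 1200.

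**Step 5: count over the window.** Take a participant who has reached 1600 and a 3-day interruption starting on day d = 50, ..., 83 (34 cases), with restart on R = d + 3.

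| Step interval | Day 86 dose below 1200 | Restart days concerned |
|---|---|---|
| 7 days | 34/34 | 53-86 |
| 3 days | 15/34 | 72-86 |
| 1 day | 5/34 | 82-86 |

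With weekly steps, 14/34 are at or below 400 µg (R = 73-86). The case d = 50 is on the edge, because 1600 is first taken that evening. Without it the counts are 33/33, 15/33 and 5/33.

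**Step 6: who can be affected.** All 379 ex-placebo participants titrate in the open-label study and are in both analysis sets. Ex-selexipag participants who titrated again in the open-label study are also exposed in the open-label set. Those who did not have no titration period there (SAP 6.10). In the combined set, the 574 treated with selexipag in the double-blind study use that study's titration. Its protocol is not among the documents, so its restart rule cannot be checked.

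**The case against.** The strongest case against the point runs as follows.

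- **The rule is a comparability choice.** SAP 6.2 ties the IMTD analysis to the 2014 and 2020 submissions. This stands as a reason not to replace the current definition. It is not a reason to leave the affected participants unidentified.
- **Weekly steps are the unfavourable assumption.** Protocol 3.4.1 leaves the pace to the investigator, and 3.3.1 allows re-titration by telephone. This stands, and it is why the counts are a range. Even daily steps leave 5 of 34 cases in the wrong category.
- **The Day 86 dose carries some information.** It is a dose the participant was taking, and after an interruption for an adverse event a lower value may be meaningful. This stands, and the fix allows for it.
- **Little depends on IMTD.** It feeds only the descriptive tables of SAP 5.5.1. It is not among the subgroups in 5.6.8, and no adverse-event, laboratory, death or survival analysis uses it. This stands.

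A reader might also infer that any interruption in the first 86 days spoils the IMTD. The documents do not support that. Early restarts finish in time, and a participant whose prior dose was 200-400 µg cannot fall to a lower non-zero category.

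**Conclusion.** The point holds for re-titrations that are unfinished on Day 86. There the SAP's rule gives a value that contradicts the protocol's notion of the tolerated dose, and no other SAP text prevents it. With weekly steps back to 1600 µg b.i.d. the condition is a restart on Day 38 or later, and the top category is lost from restart Day 52. Faster steps or a lower prior dose narrow the window.

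The 34 of 34 figure is conditional on 1600 µg having been reached, an interruption of 3 days in that window, and weekly steps. It is not a misclassification rate for the trial. The documents give no interruption frequency, so no headcount follows. An assumed 1-5% of 379 would be 3.8 to 19.0, about 4 to 19 people. Those would be people who interrupt, not people filed in the wrong category.

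The point is minor: it touches the descriptive IMTD and exposure-by-IMTD tables and no safety or survival result.

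**What to change.** In SAP 5.5.1.1:

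1. Keep the current IMTD, so that tables stay comparable with the earlier submissions.
2. Flag and count participants who on Day 86 are in an interruption of 3 days or more, or in a re-titration that has not regained the pre-interruption dose. State which dose the current rule assigns to those off drug that day.
3. Present the IMTD and exposure-by-IMTD tables a second time. For flagged participants, set IMTD to the larger of the Day 86 dose and the last b.i.d. dose before the interruption. Where the CRF reason for the interruption is an adverse event or intolerance, keep the Day 86 value. Without that exception, a dose that itself caused the interruption would be recorded as tolerated. Taking the larger value avoids lowering anyone's IMTD.

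The data should be available for the open-label study: Protocol 3.4.1 requires interruptions of 1 day or more on the study drug log and the reason in the CRF. The cost is one extra derivation and a second version of the descriptive tables.

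Separately, the restart wording in Protocol 3.2.4.1 (a recommendation) and 3.4.1 (a requirement) must be reconciled. This review takes no position on which should apply.
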